3.7.1.4 Observations/Examinations During the Antidepressant Treatment Period (Phase A)

Subjects meeting the eligibility criteria based on observations/examinations at the initiation of the antidepressant treatment period (Phase A) will proceed to the 8-week antidepressant treatment period (Phase A) to receive an antidepressant (SSRI or SNRI), which is different from the antidepressants they had been taking previously, and placebo tablets in a single-blind manner. After proceeding to the antidepressant treatment period (Phase A), the investigator or subinvestigator will perform the observations/examinations required in the antidepressant treatment period (Phase A) as specified in Table 3.7-1 Schedule of Assessments (Screening Period and Antidepressant Treatment Period [Phase A]) and record the results and findings as well as the date of visit in the source documents and the CRF. Furthermore, whether or not subjects can proceed to the double-blind period (Phase B) will be determined based on the results of observations/examinations at Week 8 of the antidepressant treatment period (Phase A), and the results of assessment will be registered in the IWRS and recorded in the source documents and the CRF. Based on an assessment at Week 8 of the antidepressant treatment period (Phase A), if the investigator or subinvestigator confirms that the subject is eligible to proceed, the subject will proceed to the double-blind period (Phase B); and if the investigator or subinvestigator determines that the subject is not eligible to proceed, the subject will be entered in the antidepressant-responder treatment-continuation period (Phase A+). Subjects meeting the criteria for proceeding to Phase B based on an assessment at Week 8 of the antidepressant treatment period (Phase A) will be randomly assigned to the brexpiprazole 1 mg/day group, the brexpiprazole 2 mg/day group, or the placebo group at a 1:1:1 ratio. Date of assignment and assignment number will be recorded in the source documents and the CRF. For subjects who do not meet the criteria for proceeding to Phase B, date of enrollment in the antidepressant-responder treatment-continuation period (Phase A+) will be recorded in the source documents and the CRF.

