3.7.4 Prior and Concomitant Medications and Therapies

The investigator or subinvestigator will examine the use of the following prior and concomitant medications and therapies. For prior and concomitant medications, the name of the drug, purpose of use (excluding prior medications used to treat the current major depressive episode), dose, frequency, route of administration, start and end dates of treatment, and treatment response (for prior medications used to treat the current major depressive episode) will be examined and recorded in the source documents and the CRF. For prior and concomitant therapies, the name of the therapy, purpose of use (excluding prior therapies used to treat the current major depressive episode), and the start and end dates of treatment will be examined and recorded in the source documents and the CRF.

- Prior medications and therapies
 - Prior medications used to treat the current major depressive episode (all antidepressants)
 - Prior therapies used to treat the current major depressive episode (psychotherapies/somatic therapies up until 6 weeks before informed consent)
 - All prior medications and therapies used within 30 days before acquisition of informed consent
- Concomitant medications and therapies
 - Concomitant medications and therapies used during the trial period (including treatments for AEs)

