4.3 Restricted Concomitant Drugs

- Ultrashort-acting sedative-hypnotic drugs that can be used in this trial are restricted to zolpidem, zopiclone, eszopiclone, and triazolam. During the treatment period (antidepressant treatment period [Phase A], and double-blind period [Phase B] or antidepressant-responder treatment-continuation period [Phase A+]), the concomitant use of only one of the aforementioned drugs is allowed; 2 or more drugs are not to be coadministered simultaneously. Change in the types of the aforementioned drugs is allowed. Regarding ultrashort-acting sedative-hypnotic drugs, the concomitant use in the double-blind period (Phase B) or the antidepressant-responder treatment-continuation period (Phase A+) is allowed but only when the drugs have been used concomitantly in the antidepressant treatment period (Phase A).
- Anticholinergic drugs for Parkinson's disease Concomitant use of anticholinergic drugs for Parkinson's disease is allowed only in the double-blind period (Phase B). Anticholinergic drugs for Parkinson's disease, for which concomitant use is allowed, are biperiden, trihexyphenidyl, profenamine, piroheptine, and mazaticol. In the case where extrapyramidal symptoms occur and use is necessary in the opinion of the investigator or subinvestigator, only one drug can be coadministered with no prophylactic use allowed. Change in the types of the aforementioned drugs is allowed.
- Antipyretic analgesic anti-inflammatory drugs, antihistamines
 The concomitant use during the treatment period (antidepressant treatment period
 [Phase A], and double-blind period [Phase B] or the antidepressant-responder
 treatment-continuation period [Phase A+]) is allowed if the drugs were being used to
 treat complications at the time of informed consent; however, no changes in dose and
 regimen are allowed unless AEs occur or the use of these drugs is considered
 unnecessary because of remission of symptoms. Furthermore, short-term concomitant
 use, including use such as a medication for colds, is also allowed. The topical external
 use of these drugs is allowed.

Note: Concomitant use of CYP2D6 inhibitors, CYP3A4 inhibitors, and CYP3A4 inducers specified in Section 4.1 Prohibited Concomitant Medications is prohibited

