7.5 Prior and Concomitant Medications

Numbers and proportions of subjects who used medications before the antidepressant treatment period (Phase A), during the antidepressant treatment period (Phase A) and the double-blind period (Phase B), and after the double-blind period (Phase B) will be determined by drug class and preferred term of the World Health Organization Drug Dictionary (WHODD) version Global B3 March 2018 overall, for each treatment group, and for the overall brexpiprazole group in the safety analysis set.

Medications used in the antidepressant treatment period (Phase A) will be similarly summarized overall and for each requisite concomitant medication in the ADT set. Medications used in the antidepressant-responder treatment-continuation period (Phase A+) will also be similarly summarized overall and for each requisite concomitant medication in the Phase A+ set.

Similar summarization will be performed for antipsychotics.

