8.3 Subgroup Analyses

For the change from baseline (Week 8 of the antidepressant treatment period [Phase A]) in MADRS total score, the same MMRM analysis as that of the primary endpoint will be performed for each of the following subgroups.

For CYP2D6 phenotype, all subjects in the placebo group will be included in each subgroup.

- Requisite concomitant medication (duloxetine, escitalopram, fluvoxamine, milnacipran, paroxetine, sertraline, venlafaxine)
- Sex (male, female)
- Age (< 55 , ≥ 55)
- Number of adequate antidepressant drug treatments (1, 2, 3)
- DSM-5 diagnosis (single episode, recurrent episode)
- Frequency of major depressive episodes (1, 2, ≥ 3)
- Duration (in months) of the current episode (\leq median, $>$ median)
- Baseline MADRS total score (\leq median, $>$ median)

- Concomitant use of ultrashort-acting sedative-hypnotic drugs in the double-blind period (Phase B) (yes or no)
- Body weight (\leq median, $>$ median)
- BMI (\leq median, $>$ median)
- CYP2D6 phenotype (IM, EM)
- Impact of COVID-19 pandemic (subjects from whom consent was obtained before 07 Apr 2020, those from whom consent was obtained on or after 07 Apr 2020)

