CT-3.2.1.6	Baseline Disease Characteristics by ADT: Paroxetine (Full Analysis Set)
CT-3.2.1.7	Baseline Disease Characteristics by ADT: Sertraline (Full Analysis Set)
CT-3.2.1.8	Baseline Disease Characteristics by ADT: Venlafaxine (Full Analysis Set)
CT-3.2.2.1	Baseline Disease Characteristics (Safety Analysis Set)
CT-3.2.2.2	Baseline Disease Characteristics by ADT: Duloxetine (Safety Analysis Set)
CT-3.2.2.3	Baseline Disease Characteristics by ADT: Escitalopram (Safety Analysis Set)
CT-3.2.2.4	Baseline Disease Characteristics by ADT: Fluvoxamine (Safety Analysis Set)
CT-3.2.2.5	Baseline Disease Characteristics by ADT: Milnacipran (Safety Analysis Set)
CT-3.2.2.6	Baseline Disease Characteristics by ADT: Paroxetine (Safety Analysis Set)
CT-3.2.2.7	Baseline Disease Characteristics by ADT: Sertraline (Safety Analysis Set)
CT-3.2.2.8	Baseline Disease Characteristics by ADT: Venlafaxine (Safety Analysis Set)
CT-3.2.4	Baseline Disease Characteristics (ADT Sample)

- CT-3.2.5 Baseline Disease Characteristics (Phase A Plus Sample)
- CT-4.1.1 Concomitant Medications: Medications Taken Prior to Start of Study Therapy (Safety Analysis Set)
- CT-4.1.2 Concomitant Medications: Medications Taken During Phase A (Safety Analysis Set)
- CT-4.1.3 Concomitant Medications: Medications Taken During Phase B (Safety Analysis Set)
- CT-4.1.4 Concomitant Medications: Medications Taken Post Study Period (Safety Analysis Set)
- CT-4.1.5 Psychiatric Concomitant Medications: Medications Taken Prior to Start of Study Therapy (Safety Analysis Set)
- CT-4.1.6 Psychiatric Concomitant Medications: Medications Taken During Phase A (Safety Analysis Set)
- CT-4.1.7 Psychiatric Concomitant Medications: Medications Taken During Phase B (Safety Analysis Set)
- CT-4.1.8 Psychiatric Concomitant Medications: Medications Taken Post Study Period (Safety Analysis Set)
- CT-4.2.1 Concomitant Medications: Medications Taken During Phase A (ADT Sample)
- CT-4.2.2 Concomitant Medications: Medications Taken During Phase A Plus (Phase A Plus Sample)
- CT-4.2.3 Psychiatric Concomitant Medications: Medications Taken During Phase A (ADT Sample)
- CT-4.2.4 Psychiatric Concomitant Medications: Medications Taken During Phase A Plus (Phase A Plus Sample)
- CT-4.4.1 Summary of Major Protocol Deviations by Center and Type of Deviation (Randomized Subjects)
- CT-4.4.2 Summary of Major Protocol Deviations by Center and Type of Deviation (Non-randomized Subjects)

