CT-6.7.1 Summary of Mean Change From Baseline (End of Phase A) to Phase B by Study Week in MADRS Total Score by Duration of Current Episode: \leq Median - MMRM (Full Analysis Set)

CT-6.7.2 Summary of Mean Change From Baseline (End of Phase A) to Phase B by Study Week in MADRS Total Score by Duration of Current Episode: $>$ Median - MMRM (Full Analysis Set)

CT-6.8.1 Summary of Mean Change From Baseline (End of Phase A) to Phase B by Study Week in MADRS Total Score by Baseline MADRS Total Score: \leq Median - MMRM (Full Analysis Set)

CT-6.8.2 Summary of Mean Change From Baseline (End of Phase A) to Phase B by Study Week in MADRS Total Score by Baseline MADRS Total Score: $>$ Median - MMRM (Full Analysis Set)

CT-6.9.1 Summary of Mean Change From Baseline (End of Phase A) to Phase B by Study Week in MADRS Total Score by Ultrashort-acting Sedative-hypnotic Drugs: Present - MMRM (Full Analysis Set)

CT-6.9.2 Summary of Mean Change From Baseline (End of Phase A) to Phase B by Study Week in MADRS Total Score by Ultrashort-acting Sedative-hypnotic Drugs: Absent - MMRM (Full Analysis Set)

CT-6.10.1 Summary of Mean Change From Baseline (End of Phase A) to Phase B by Study Week in MADRS Total Score by Baseline Weight: \leq Median - MMRM (Full Analysis Set)

CT-6.10.2 Summary of Mean Change From Baseline (End of Phase A) to Phase B by Study Week in MADRS Total Score by Baseline Weight: $>$ Median - MMRM (Full Analysis Set)

CT-6.11.1 Summary of Mean Change From Baseline (End of Phase A) to Phase B by Study Week in MADRS Total Score by Baseline BMI: \leq Median - MMRM (Full Analysis Set)

CT-6.11.2 Summary of Mean Change From Baseline (End of Phase A) to Phase B by Study Week in MADRS Total Score by Baseline BMI: $>$ Median - MMRM (Full Analysis Set)

CT-6.12.1 Summary of Mean Change From Baseline (End of Phase A) to Phase B by Study Week in MADRS Total Score by CYP2D6 Metabolism Status: IM - MMRM (Full Analysis Set)

CT-6.12.2	Summary of Mean Change From Baseline (End of Phase A) to Phase B by Study Week in MADRS Total Score by CYP2D6 Metabolism Status: EM - MMRM (Full Analysis Set)
CT-6.13.1	Summary of Mean Change From Baseline (End of Phase A) to Phase B by Study Week in MADRS Total Score by Impact of COVID-19 Pandemic: Subjects Completed/Discontinued before 07APR2020 - MMRM (Full Analysis Set)

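### SAP 8.3 splits the primary MMRM by hypnotic use during Phase B, which is observed after randomisation; a split by use before randomisation would remove a possible source of bias at little cost

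*SAP*

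**What the plan says.** SAP 8.3 fits the primary model for change in MADRS total score separately within the levels of 13 factors. One factor is "Concomitant use of ultrashort-acting sedative-hypnotic drugs in the double-blind period (Phase B) (yes or no". The matching table, CT-6.9.1 in SAP Appendix 5, is titled in part "MADRS Total Score by Ultrashort-acting Sedative-hypnotic Drugs: Present" and does not say when use is measured; nor does its companion, CT-6.9.2.

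Protocol 3.7.1.4 places randomisation at the end of Phase A: subjects who qualify "at Week 8 of the antidepressant treatment period (Phase A) will be randomly assigned to the brexpiprazole 1 mg/day group" or to one of the other two arms.

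Protocol 4.3 restricts these hypnotics. Use in Phase B "is allowed but only when the drugs have been used concomitantly in the antidepressant treatment period (Phase A").

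Protocol 3.7.4 has sites record, for prior and concomitant drugs, "dose, frequency, route of administration, start and end dates of treatment". SAP 7.5 tabulates medications by arm in the safety set, grouped by class and preferred term; the counts of users "during the antidepressant treatment period (Phase A) and the double-blind period (Phase B), and after the double-blind period (Phase B) will be determined". CT-4.1.3 covers all Phase B medications, and CT-4.1.7 is titled "Psychiatric Concomitant Medications: Medications Taken During Phase B (Safety Analysis Set").

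**The concern.** A subgroup contrast keeps the protection of randomisation only if treatment cannot affect who is in the subgroup. Phase B hypnotic use is the one factor in SAP 8.3 that can fail this test. The other 12 are history, demographics, genotype, the Phase A antidepressant, consent date or baseline values. SAP 8.3 gives no time point for weight and BMI, but SAP 7.2 and the titles of CT-6.10 and CT-6.11 make them baseline values.

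A link between treatment and hypnotic use is plausible. Reduced sleep is one of the ten MADRS items (Protocol 3.7.2.1), so a drug that changes the outcome could also change the need for a hypnotic. The documents do not show that it does. If it does, each stratum compares subjects selected differently by arm, and the two contrasts could suggest a difference in effect that is not real, or conceal one that is. If it does not, there is no bias.

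A separate matter: the titles of CT-6.13.1 and CT-6.13.2 define the pandemic subgroup by completion or discontinuation date ("Impact of COVID-19 Pandemic: Subjects Completed/Discontinued before 07APR2020"), whereas the SAP 8.3 text uses consent date. That mismatch should be corrected, but it is not part of this point.

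**Working it through.** **Who can change stratum.** New users are barred in Phase B. If 'yes' means any use in Phase B, a subject still using when Phase B starts is 'yes' in every arm, and stopping later does not alter that. A subject with no Phase A use is 'no' in every arm, deviations aside. This leaves Phase A users who are lapsed or intermittent at Week 8. Protocol 4.3 requires use in Phase A, not continuous use or use at Week 8, so the route is narrowed but not closed.

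**Planning values.** The effect of -2.4, SD of 7.7 and 240 per arm come from SAP 4. They reproduce the plan's 218 per group: the normal approximation gives 217, and the t distribution gives power 0.8996 at 217 and 0.9009 at 218. That figure is not in dispute.

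**Illustration.** Every behavioural input below is assumed.

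- Outcome: Y = -2.4T + 7.7e, with T = 1 on active treatment and the same true effect in everyone.
- Sleep need: S = ρe + √(1 - ρ²)·z + shift·T.
- 40% of subjects are Phase A users. A share k of them is fixed 'yes'; the rest are 'yes' if S > c, with c set so that a proportion p of them use on placebo.
- Let a = c - shift·T and q = 1 - Φ(a).
- Mean e in 'yes' = (1 - k)ρφ(a) / [k + (1 - k)q].
- Mean e in 'no' = -0.4(1 - k)ρφ(a) / [0.6 + 0.4(1 - k)(1 - q)].
- Contrast = -2.4 + 7.7 × (mean e on active - mean e on placebo).
- Grid: p = 0.2, 0.5, 0.8; ρ = 0.2, 0.6; shift = -0.312 (that is, -2.4/7.7), -0.312ρ, +0.3.

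One cell in full, with k = 0.5, p = 0.2, ρ = 0.6 and shift = -0.312:

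- Placebo: a = 0.842, φ = 0.2800, q = 0.2; mean e = 0.3 × 0.2800 / 0.6 = 0.1400.
- Active: a = 1.154, φ = 0.2051, q = 0.1243; mean e = 0.3 × 0.2051 / 0.5622 = 0.1094.
- 'Yes' contrast = -2.4 + 7.7 × (0.1094 - 0.1400) = -2.64.
- 'Yes' subjects: 240 × 0.4 × 0.6 = 57.6 on placebo and 240 × 0.4 × 0.5622 = 54.0 on active. The 95% half-width is 1.96 × 7.7 × √(1/57.6 + 1/54.0) = 2.86.

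Changing only p to 0.8 gives -2.18, so the sign of the bias reverses under the same shift. No direction can be claimed.

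Full grid:

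| Phase A users still using at Phase B start (k) | 'Yes' contrast | Largest departure | 95% half-width at the extremes | 'No' contrast | Largest departure |
|---|---|---|---|---|---|
| None | -3.45 to -1.25 | 1.15 | 4.5 to 5.6 | -2.56 to -2.23 | 0.17 |
| Half | -2.64 to -2.18 | 0.24 | 2.3 to 2.9 | -2.49 to -2.30 | 0.10 |
| 80% | -2.48 to -2.33 | 0.08 | 2.2 to 2.4 | -2.44 to -2.36 | 0.04 |
| All | -2.4 | 0 | – | -2.4 | 0 |

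The first row is an extreme case, with only 12 to 28 'yes' subjects per arm at its limits. With no treatment effect on use, both contrasts are -2.4 in every row.

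**Does the alternative split remove the problem?** A separate simulation (2,000,000 subjects per arm, Week 6 change only, true effect -2.4) let Phase A users stop but not start. A split by Phase A use returned -2.37 to -2.43 in every scenario, which is simulation noise. The Phase B split departed from -2.4 by up to about 1.4 in 'yes' and 0.4 in 'no' when the arms had different stopping rates (10% against 20–30%). On the any-use reading, those figures apply only to subjects who take no hypnotic at all in Phase B, so they should not be added to the table above.

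**The case against.** The strongest reply is that Protocol 4.3 nearly closes the route. Anyone using at the start of Phase B is 'yes' whatever the arm, and nothing in the documents says that lapsed or intermittent users are numerous or would behave differently by arm. Every departure in the table is well inside the sampling error of its own contrast, and the 1.15 figure needs no Phase A user to be still using at the start of Phase B. The analysis lies outside the fixed-sequence test, and the by-arm medication tables would let a reader see an imbalance. The pre-randomisation split also answers a different question: it describes prior or ongoing users, not the effect alongside concurrent hypnotic use.

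Most of this stands, and it is why the point is minor. It does not remove the point. The route is narrowed, not closed. The by-arm tables could reveal an imbalance in use, but the contrasts would still be conditioned on a value observed after randomisation. The titles of CT-6.9.1 and CT-6.9.2 do not warn the reader of that.

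**Conclusion.** The concern holds as a minor improvement. The classifier is observed after randomisation, and a pre-randomisation split removes that route to bias. Whether any bias exists depends on two things the documents do not give: how many Phase A users are lapsed or intermittent at Week 8, and whether treatment alters their hypnotic use. The illustrated departures, from nil to 1.15 MADRS points in 'yes' and from nil to 0.17 in 'no', rest on assumed behaviour and the any-use reading. They are not bounds. They fall to at most 0.08 and 0.04 if 80% of Phase A users are still using when Phase B starts. The primary, secondary and fixed-sequence results are untouched.

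**What to change.** In SAP 8.3, define this subgroup by hypnotic use before randomisation: any use in Phase A up to the Week 8 visit, taken from the recorded start and end dates. Use ongoing at the Week 8 visit would be an equally valid definition and closer to the present factor; the SAP should name one. Retitle CT-6.9.1 and CT-6.9.2 to state the timing.

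If the Phase B version is kept, show it beside the new one, label it descriptive and non-randomised, and read it with CT-4.1.3 and CT-4.1.7.

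The cost is SAP wording and two table titles, with no new data. The small loss is that the new split no longer describes the effect alongside concurrent Phase B use.
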